USPS	United States Parcel Service

Note to Reviewers: The health care professional portion of the study (related to the secondary objective and study aim 3) will be evaluated as a separate study submission.

1 OBJECTIVE, SPECIFIC AIMS, BACKGROUND, AND SIGNIFICANCE

1.1 Objective

1.1.1 Primary

To demonstrate that patients who are trained on and use the MyDoseCoach titration (MDC-T) phone application (app) to titrate insulin will have greater improvements in hemoglobin A1c (HbA1c) and more likely to achieve glycemic control at 3 months as compared to usual care practice, and those who do attain glycemic goals, are able to maintain glycemic control for an additional 3 months using the MDC Maintenance (MDC-M) app.

1.1.2 Secondary

To examine the feasibility of integrating digital solutions into clinical workflow and acceptability of MDC-T and MDC-M by health care professionals (HCPs) and patients.

1.1.3 Hypothesis

Patients using MDC-T will reach individualized fasting plasma glucose (FPG) and HbA1c targets and MDC-M will help patients to maintain glycemic targets at 6 months from baseline.

1.2 Specific Aims

1.2.1 Aim 1

To determine the effect of MDC-T on helping patients with T2DM, who are new to titrating insulin, to improve glycemic control and achieve target goals as compared to patients who titrate insulin with traditional usual care processes.

1.2.2 Aim 2

To determine if patients with T2DM can maintain glycemic control when reaching target goals after using insulin titration guided by the MDC-T.

1.2.3 Aim 3

To examine the feasibility of integrating digital solutions into clinical workflow and the acceptability of MDC (T and M) by HCPs and patients.

1.3 Background

1.3.1 Type 2 Diabetes Mellitus and Challenges in Meeting Treatment Goals

Despite the increasing body of knowledge of diabetes treatment strategies, a majority of patients with T2DM are still in a persistent state of poor glycemic control and unable to meet target goals [1]. Inertia surrounding insulin initiation and titration is a specific problem. Physicians may be reluctant to initiate and titrate insulin owing to a belief about patient risk, including associated concerns about patient competence, and resource issues [2,3].

Most patients with T2DM are seen in a primary care (PC) setting [4], which presents challenges in overcoming clinical inertia and facilitation of intensified therapies. A provider's decision to delay therapy in many cases may be related to fears over inadequate time, educational resources and added workload [5-8]. A survey of physician attitudes found that they consider diabetes more difficult to treat than other chronic diseases as it requires more monitoring and medication adjustment to achieve treatment goals [7]. Physicians also report that there is inadequate support for the increased time and effort required for treating diabetes patients, and neither clinics nor patients can afford what it takes for comprehensive care [5-9].

Various approaches have been proposed to help overcome clinical inertia, including support of patient self-management, and education for both physicians and people with diabetes [10-13]. It has been recommended that patient education should specifically target the concerns surrounding the intensification of therapy [14,15]. Our team conducted a 12-month cluster randomized controlled trial *Practice Intensification via Office Transformation* (PIVOT) to explore the feasibility and effectiveness of a diabetes care and education specialist (DCES)-led provider/patient intervention to support pharmacotherapy advancement in PC. Findings support the value of DCES-led education to reduce clinical inertia while highlighting the heterogeneity of practice models with recognition that clinical inertia in PC is a complex issue that requires continued exploration [13,16].

In an era of more tightly controlled health care resources, health systems and payers, including the University of Pittsburgh Medical Center (UPMC) and its' integrated payer the UPMC Health Plan, have already begun to seek ways to examine approaches that shift roles and include non-physician practitioners to address the problems. In partnership and supported by our own UPMC Health Plan, a *Diabetes High Risk Program*, was designed for diabetes patients at high risk for complications and unplanned care to receive DCES planned visits in underserved rural and urban practices. Two DCESs were introduced as members of PC teams, identified and provided individualized self-management education to DM patients considered at high risk (i.e., hemoglobin A1C \geq 9%, DM-related emergency room visit or hospitalization, or reported barriers to care, e.g. medication adherence). Patients who participated in the program had significant improvements in glycemia that were sustained for one year [17].

DCESs are well suited to support skills necessary to achieve glycemic target goals and considered experts in teaching patients medication taking skills [18,19]. Presently, paper-based guides are available in which clinicians/educators rely on to help their patients in determining and recording appropriate insulin doses. The paper-based titration tool is prepared as a worksheet with steps to determine the next insulin dose. Determining insulin doses in practice

today is often a matter of trial and error, as the dose is tailored to a patient's individual therapeutic needs. A provider determines an appropriate dosage for the first time based on weight and blood glucose records. The patient is then expected to consult their provider and/or a DCES (if available) to teach him/her how to adjust the insulin dose, based on their BG levels and given a paper-based scale/algorithm to guide them on dose change doses. The patient is expected to assume the "lion's share" of the effort to initiate and titrate insulin using their "worksheet" with limited or unpredictable follow up. Unfortunately, this process often sets the stage for reluctance and fear of insulin initiation and delays titration with implications for long-term poor self-management and adherence.

1.4 Significance

Appropriate titration of basal insulin and ensuring that patients adhere to health care professional (HCP) recommended therapeutic regimens is critical to the achievement and maintenance of glycemic targets in the management of T2DM. Therefore, Sanofi has developed the MDC (T&M) app for guiding titration and supporting maintenance of therapy.

1.4.1 MyDoseCoach Application

MDC is an FDA-approved digital solution comprising a smartphone app for people with T2DM and web portal for healthcare professionals (HCPs). The **MDC Basal Titration Module** (MDC-T) provides a digital alternative to the manual titration model that is typically used for dose modification of longer-acting basal insulin for patients with T2DM. This allows the HCP to tailor the dosing instructions to the individual patient based on the HCP's independent professional judgment. The HCP defines an individualized longer-acting basal insulin titration plan that is used in MDC to give dose recommendations to the user based on their FBG readings and hypoglycemic event data. MDC provides similar functionality as a paper-based tool, while automatically calculating the median FBG value and instructing the patient on the next appropriate insulin dose according to a dose plan and dose adjustment rules set by their HCP.

[figure not shown]
The MDC app is also designed to support patients in maintaining proper insulin dosing to help ensure ongoing glycemic control. Like the titration module, the **MDC Maintenance Module** (MDC-M) is intended for use by HCP's and patients to enable logging of insulin and non-insulin medication use and BG measurements and provide dosing and measurement reminders.

2 RESEARCH DESIGN AND METHODS

2.1 Classification and Methodological Designs

This study is a 6-month open label non-randomized trial with a prospective intervention group and a retrospective usual care group that includes two phases: Phase 1 (titration) will be used to determine effectiveness of MDC-T during insulin titration after 3 months. This is followed by Phase 2 (maintenance), a 3-month observational period for patients from the intervention group who reach titration targets, to determine effectiveness of their use of the MDC-M in helping patients maintain their glycemic targets. An overview of the study design in shown in the following figure.

Figure 2.1. Study Design

2.2 Detailed Description of Study Design

2.2.1 Setting

UPMC, headquartered in Pittsburgh, Pennsylvania, is one of the largest integrated health systems in the US, with more than 30 academic, community and specialty hospitals and 600 outpatient sites serving diverse populations throughout the region and beyond. UPMC is closely affiliated with the University of Pittsburgh and together support training for medical residents, clinical trials and other academic research. UPMC's reach and impact are extended through its Health Plan Insurer Services Division, which partners with UPMC and additional community network providers. UPMC is also a recognized innovator in health technology, including developing and applying data-driven approaches to provide patient-centered care. Central to these efforts is UPMC's Clinical Data Warehouse that contains all data points documented within the EMR system for every patient entering a UPMC facility, including but not limited to office visits, hospitalizations, medications, labs, and geographical information. The Department of Clinical Analytics aims to empower UPMC's health care professionals by providing access to interpretable visualizations of their own patient data. Such applications have facilitated both operational- and research-based endeavors, that ultimately improve patient care. For these reasons and more, UPMC provides an ideal "community laboratory" to examine methods that promote access and best practice to the patients it serves.

2.2.2 Heath Care Providers

HCPs who deliver diabetes care and education (e.g., endocrinologists, nurse practitioners, physician assistants and/or DCESs) at participating study sites will be invited to recruit/consent patients, train and support patients on use of the MDC, obtain study data as well as provide their own perspectives on the MDC app. Prior to initiating patient enrollment, participating HCPs will be fully trained on the MDC app and all study procedures, roles and responsibilities.

2.2.3 Intervention Group

Phase 1 (Titration)

Baseline Visit

Patients assigned to the intervention group will meet with a DCES and receive insulin therapy education according to current standard of care procedures (e.g., how to use an insulin pen, when and where to administer insulin, etc.). Whereas DCESs typically provide patients with written titration instructions prepared by the physician provider, for the intervention, DCESs, another HCP and/or a trained clinical research coordinator will train patients to use MDC-T for titration guidance. The physician provider will prepare an individualized titration algorithm, including a dose plan and dose adjustment rules that will be embedded in MDC-T. The DCES, another HCP, and/or clinical research coordinator will demonstrate to the patient how to use the MDC Titration Module to determine and guide dosing adjustments.

All patients will be asked to complete a baseline survey to assess behavioral and psycho-social factors that may influence diabetes self-management. In addition, patients will receive a threemonth supply of insulin pens (Lantus (U100) Solostar Pen or Toujeo (U300) Solostar Pen, as per treating Physician).

Patients will be instructed to return for a three-month follow-up clinic visit, as is standard of care for patients new to insulin.

Month 3 Visit

At the three-month appointment, the DCES or another HCP will assess the patient's experiences with titration and MDC-T, which will be documented using a study-specific survey. If the patient successfully reached their glycemic target, they will be invited to participate in Phase 2 of the study (maintenance).

For those patients who do not reach target at 3 months, the DCES/HCP will partner with the patient (and physician provider, as needed) to assess the patient's ability and interest in continued use of the MDC-T app and determine the best course of action (either return to usual care or continued participation in the study). If deemed eligible, the patient will continue to have access to the MDC-T app with continued guidance from their respective HCP, in regards to insulin therapy recommendations. They will be asked to complete follow-up surveys at months 3 and 6, as well as permit access to pertinent medical record information (e.g., HbA1c values) for the duration of the study. Patients who stay in the study and continue to use the MDC-T app will receive another three-month supply of insulin pens (Lantus (U100) Solostar Pen or Toujeo (U300) Solostar Pen, as per treating Physician).

Phase 2 (Maintenance)

Patients who are successful in reaching their glycemic target and agree to continue participation, will be transitioned into Phase 2 of the study at their three-month clinic visit. At this time, the HCP (endocrinology provider and/or DCES) will introduce and train patients how to use the MDC-M app to support glycemic control. Patients will receive another three-month supply of insulin pens (Lantus (U100) Solostar Pen or Toujeo (U300) Solostar Pen (as per treating Physician) and asked to return for the final follow-up visit at six months (routine clinic visit). They also will be asked to complete follow-up surveys at months 3 and 6 to assess changes in behavioral and psychosocial factors that influence diabetes self-management as well as their acceptability and satisfaction with their experience using the MDC app. When possible, surveys will be completed at clinic visits. However, surveys may also be made available electronically or via mail should visits occur remotely (e.g., via telemedicine) or a patient cannot complete at a face-to-face visit (e.g., time constraints).

The DCES and endocrinology provider will be available throughout the course of the study to respond to any question or concerns that the patient may have regarding insulin titration, insulin dosing, and the MDC app specifically.

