3.2.2 Usual Care Group

- Adult male and female patients 18 to 75 years old
- HbA1c > 7.5%
- Started on basal insulin in a UPMC Diabetes Outpatient facility within the past three years of study start

• Has blood glucose data available in EMR (At least two HbA1c measurements corresponding to baseline and a subsequent time point after insulin titration) FBG readings)

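### DCES insulin teaching and ongoing access are guaranteed to intervention patients but neither required, recorded nor matched in the retrospective controls, so an HbA1c difference cannot be separated from any difference in DCES exposure

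*Combined protocol and SAP*

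**What the plan says.** **Intervention arm.** Under the Baseline Visit, section 2.2.3 states: "Patients assigned to the intervention group will meet with a DCES and receive insulin therapy education". The sentence goes on to describe this education as current standard of care. The same section describes what the app replaces: "Whereas DCESs typically provide patients with written titration instructions prepared by the physician provider". At the end of section 2.2.3: "The DCES and endocrinology provider will be available throughout the course of the study to respond to any question or concerns", which covers titration and dosing as well as the app.

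**Control arm.** Section 3.2.2 sets age, baseline HbA1c, EMR glucose data and this setting criterion: "Started on basal insulin in a UPMC Diabetes Outpatient facility within the past three years of study start". It has no criterion on DCES contact or titration teaching. The Control Group text in section 2.4.1 names HbA1c, FBG, blood pressure, cholesterol, BMI, meter readings and hypoglycemic events. It names neither visits nor education. The study calendar (2.2.5) lists provider and endocrinology escalation visits at months 3 and 6, but not DCES contact at insulin start.

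**Analysis.** Section 2.6.2 builds the propensity score from age, gender, baseline BMI and baseline HbA1c, with race and number of comorbid conditions as options. The mixed model adds baseline FBG and a random effect for matched pair.

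**What the contrast is meant to be.** The table in section 2.3 puts only the app under study research, and section 6.1 says that technology and questionnaires are the only additions to usual care.

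**The concern.** If the app is the only thing that differs, both arms must have had the same education. That is assured by design in one arm and left to chance in the other. Matching on age, gender, BMI and HbA1c balances who the patients are. It cannot balance what care they were given after insulin was started.

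The protocol itself gives reason to ask. Section 1.3.1 says that the patient in practice today is "expected to consult their provider and/or a DCES (if available", and describes later follow-up as something that cannot be relied on. The same section reports that patients in a DCES program had "significant improvements in glycemia that were sustained for one year". So the protocol regards DCES contact as active and as variable in ordinary care.

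At stake is attribution. A lower 3-month HbA1c in the intervention arm could reflect the app, more DCES contact, or both. With the data now listed for controls, nobody could tell afterwards which.

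**Working it through.** **1. The plan's own figure.** Inputs from section 2.6.1: SD of the 3-month change 1.5, 109 patients per arm. The 95% level is from section 2.6.2.

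- SE = 1.5 × √(2/109) = 1.5 × 0.1355 = 0.203.
- Half-width = 1.96 × 0.203 = 0.398, which agrees with the stated ±0.40.
- Conversely, n = 2 × (1.96 × 1.5 / 0.40)² is just over 108, so 109 per arm.

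The figure is right. It covers sampling error only and says nothing about a systematic difference in care.

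**2. Bias from unequal DCES teaching.** Let e be the effect of DCES teaching on 3-month HbA1c, in points, and u the share of controls without equivalent teaching. In the intervention arm that share is 0 by design. If effects add, the expected difference between arms is the app effect plus e × u, so the bias is e × u.

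The documents give neither e nor u. The values below are assumptions.

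| u (controls without teaching) | e = 0.2 | e = 0.6 |
|---|---|---|
| 0% | 0 | 0 |
| 20% | 0.20 × 0.2 = 0.04 | 0.20 × 0.6 = 0.12 |
| 60% | 0.60 × 0.2 = 0.12 | 0.60 × 0.6 = 0.36 |

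**3. What this does to the interval.** With no app effect and bias b, the chance that the 95% interval excludes zero is Φ(b/0.203 − 1.96) + Φ(−b/0.203 − 1.96), by the normal approximation. With u = 50%:

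| e | b | Chance of excluding zero (nominal 5%) |
|---|---|---|
| 0.2 | 0.10 | 7.8% |
| 0.3 | 0.15 | 11.4% |
| 0.5 | 0.25 | 23.4% |

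With u = 0 it stays at 5%. The whole question turns on u, which the plan does not collect.

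**The case against.** The strongest reply is that no imbalance has been shown. Section 2.2.3 calls the education standard of care and says that DCESs typically hand over the physician's written instructions. Controls come from diabetes specialty clinics (2.2.4), where such teaching may well be routine. No passage says that any control went without it. This stands, and it is why zero bias belongs in the range.

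A reader might go further and infer that the trial compares app plus education with no education, and that the bias must favour the app. The documents do not support either step:

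- The remarks in section 1.3.1 about DCES availability and follow-up describe practice in general, not these clinics.
- The DCES program cited there consisted of planned visits for high-risk primary care patients. It is reported without a comparator or an effect size, so it makes an effect plausible but does not measure the effect of one baseline session.
- Ongoing access in section 2.2.3 means availability for questions, not scheduled contact. The month-3 assessment falls at the visit where the primary outcome is due and can hardly influence it.
- Controls started insulin in specialty clinics, whereas section 3.1 also recruits intervention patients from primary care practices and inpatient units. More specialist contact among controls would push the other way.

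A second reply is that usual care as delivered, with whatever DCES contact it includes, is a legitimate comparator. The objective in section 1.1.1 is framed against usual care practice. This also stands: making a DCES visit an entry criterion for controls would change the comparator. It does not answer the attribution question, because sections 2.3 and 6.1 present the app as the only added treatment component.

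**Conclusion.** The point holds as a gap in design and measurement, not as a demonstrated bias. DCES exposure is fixed in one arm and unrequired, unlisted and unadjusted in the other, so the planned analysis cannot separate the app from any difference in that exposure.

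Under the assumed effects of 0.2 to 0.6 points and 0 to 60% of controls untaught, the bias from this source is 0 to 0.36 points. The upper end is close to the full ±0.40 half-width. These limits are chosen for illustration and rest on additive effects. The net direction once specialist contact is counted is not settled by the documents. The sample size calculation is unaffected.

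**What to change.** **Section 2.4.1, Control Group.** Add abstraction of any documented DCES or equivalent insulin-teaching encounter within a stated window around the index date. Tabulate DCES and provider contacts through month 3 in both arms. Describe these contacts but do not adjust for them, since contacts after baseline may themselves result from the way titration was guided.

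**Section 2.6.2.** Keep the primary comparison against usual care. Pre-specify a sensitivity analysis of the 3-month HbA1c difference that re-matches intervention patients only to controls with such an encounter, and state in advance what counts as agreement with the primary result. Attribute an effect to the app alone only if the two agree. Otherwise describe the contrast as app plus DCES support versus specialty usual care.

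Do not enter DCES contact (yes/no) in the propensity model. It is constant in the intervention arm, so its absence would identify controls perfectly. Requiring a match on it is the same as restricting to taught controls.

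**Cost.** Some extra EMR abstraction, and possibly a smaller control pool with a wider interval in the sensitivity analysis. By the formula above, 80 pairs would give 1.96 × 1.5 × √(2/80) = 0.46 and 60 pairs 0.54 (illustrative counts; the pool size is not given). Section 2.2.1 says that the data warehouse holds office visits but does not name DCES encounters, so first confirm that they can be identified. Equal teaching at insulin start would not guarantee equal access afterwards, which is why the contact table is needed as well.

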2.2.5 Study Calendar

Clinical Care/EMR Data Abstraction			
Demographics ⁵	Х		
Patient History ⁶	Х		
Vital signs ⁷	Х	Х	Х
Lab work ⁸	Х	Х	Х
Self-monitoring blood glucose (SMBG)		Х	Х
Provider visits (and Endocrinology escalation visits)		х	Х
Hypoglycemic events	Х	Х	Х
Hospital stays	Х	X	Х
Adverse events	Х	X	Х

1. Education on MDC-M app only for those participants who were able to reach target FBG/A1c transition to maintenance.

2. Diabetes Medication System Rating Questionnaire-Short Form (DMSRQ-SF), Diabetes Distress Scale (DDS17) at all time points; Usability and Satisfaction surveys as 3 and 6 months.

3. Health care provider perspectives and experiences on insulin dosing survey at baseline and usability and satisfaction survey at 3 months and completion of the study.

4. Participant name, age, gender, race, ethnicity, contact information, location, marital status, employment status, education level, health insurance information

5. Diabetes duration, diabetes-related medication, diabetes-related hospitalizations, hypoglycemic events within the past year, co-morbidities

6. Blood pressure, weight, BMI

7. Fasting blood glucose, HbA1c, cholesterol, lipids (if available in clinical records); baseline values may have been collected and recorded up to nine months prior to study start (e.g., lipid panels are usually conducted once a year).

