2.3 Insulin Management System

Clinical and research components of clinical care are delineated in the table below. The information included in the "Routine Clinical Care (not on study)" column represents the routine care a patient with diabetes would undergo when starting an insulin regimen without being on a research study. The information in the "Routine Clinical Care (on study)" column represents the procedures the research participants will receive as routine clinical care while on this study and not related to the research component. The procedures in the "Study Research" column represents the investigational component of this research study being evaluated and would not be included as part of the patient's routine clinical care.

	Routine Clinical Care	Routine Clinical Care		
	(not on study)	(on study)	Study Research	
Phase 1 – Titration	 Insulin pen (or syringe and needles) Paper dosage algorithm Blood glucose meter 	 Insulin pen (Lantus (U100) Solostar Pen or Toujeo (U300) Solostar Pen (as per treating Physician)) Dosage algorithm Blood glucose meter 	 Use of MDC-T app (to support insulin dosage algorithm) 	

Table. Clinical and Research Components of Patient Visits

Maintenance Block	• Iood glucose heter	Insulin pen (Lantus (U100) Solostar Pen or Toujeo (U300) Solostar Pen (as per treating Physician))Blood glucose meter	•	Use of MDC-M app
---------------------	-------------------------	---	---	------------------

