11 COSTS AND PAYMENTS

11.1 Costs

Item	Cost/Supplier
MyDoseCoach App (Titration and Maintenance)	Available free of charge from either the Google Play Store for android devices or App Store for iOS Apple devices
Lantus (U100) Solostar Pen or Toujeo (U300) Solostar Pen	Supplied free of charge by Sanofi

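### The 3-month HbA1c contrast compares MDC-T plus a free insulin supply with usual care, but the plan presents it as the effect of the app alone

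*Combined protocol and SAP*

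**What the plan says.** **What the intervention arm receives.** At baseline, "patients will receive a threemonth supply of insulin pens" (2.2.3, Baseline Visit). At month 3, those entering maintenance get a second supply: "Patients will receive another three-month supply of insulin pens" (2.2.3, Phase 2). Patients who missed target but stay on MDC-T also get one. Section 11.1 describes the pens as "Supplied free of charge by Sanofi".

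**What the controls received.** They are past patients found in the EMR: "Started on basal insulin in a UPMC Diabetes Outpatient facility within the past three years of study start" (3.2.2). Sections 2.2.4, 2.4.1 and 3.2.2 describe no supply for them and do not say how they obtained or paid for insulin. In the 2.3 table, the off-study column for titration begins "Insulin pen (or syringe and needles" and names neither a product nor a supply.

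**How the plan labels these elements.** The 2.3 table places the study pens under routine clinical care on study. Its Study Research column, which "represents the investigational component of this research study being evaluated", has one Phase 1 entry: "Use of MDC-T app (to support insulin dosage algorithm". Section 6.1, on psychological risk, says that only technological support and questionnaires are added to usual care.

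**What the result is credited to.** Section 1.1.1 speaks of patients trained on and using MDC-T. Aim 1 (1.2.1) and 2.4.1 attribute the glycemic effect to MDC-T.

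**Adjustment.** The propensity score in 2.6.2 uses age, gender, baseline BMI and baseline HbA1c, with race and comorbidity count optional. The mixed model adds baseline FBG and a random effect for matched pair. Insurance is on the study calendar's demographics list ("marital status, employment status, education level, health insurance information", 2.2.5) but is not in the score.

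**The concern.** Free insulin can make it easier to obtain and keep taking the drug, and so could lower HbA1c even if the app did nothing. The supply is a study provision that only the intervention arm is described as receiving, so the two arms differ in at least two ways, while the plan names one. If the plan is followed as written, the report would state a combined effect as an app effect. A reader deciding whether to adopt the app without free insulin would then be relying on a comparison that was never made. At stake is what the trial may conclude, not how precisely it estimates.

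**Working it through.** **1. The plan's own figure.** Inputs from 2.6.1: SD of the 3-month change 1.5, 109 per arm; 95% confidence level from 2.6.2.

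- SE = 1.5 × √(2/109) = 0.203
- Half-width = 1.96 × 0.203 = 0.398 (0.400 using t with 216 df)
- Inverse: n = 2 × (1.96 × 1.5 / 0.40)² = 108.04, rounded up to 109

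The stated ±0.40 reproduces. The present point does not change it.

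**2. What the contrast identifies.** Every intervention patient has both the app and the supply. As far as the documents show, every control has neither. Apart from any residual confounding:

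expected difference = app effect + supply effect (including any interaction between them)

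Only the sum is estimable. No patient has one without the other, so a supply indicator would be the same variable as study arm. Neither the propensity score nor the mixed model in 2.6.2 can split the two, whatever covariates are added.

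**3. Illustrative size (assumptions, not document figures).** The documents give no effect of free supply on HbA1c. Suppose 10-20% of controls had cost-related gaps, each costing 0.5-1.0 points at 3 months, and that free supply removes all of them.

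- Low corner: 0.10 × 0.5 = 0.05, which is 0.05/0.40 = one eighth of the stated half-width
- High corner: 0.20 × 1.0 = 0.20, which is 0.20/0.40 = one half

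**4. What that would do to an app-specific reading.** Let the true app effect be zero and the supply effect be b. The chance that the 95% CI lies wholly on the intervention's side is Φ(b/SE − 1.96). Coverage of the app effect is Φ(1.96 − b/SE) − Φ(−1.96 − b/SE).

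| Assumed b | CI favours intervention (nominal 2.5%) | Coverage of app effect (nominal 95%) |
|---|---|---|
| 0.05 | 4.3% | 94.3% |
| 0.10 | 7.1% | 92.2% |
| 0.20 | 16.5% | 83.4% |

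These use the SE from step 1, which ignores within-pair correlation. With a correlation of 0.2 (assumed), the half-width is 1.96 × 1.5 × √(2 × 0.8/109) = 0.356, so a given b weighs somewhat more.

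**5. Which supply matters.** The primary endpoint (2.5.1) is at 3 months. The second supply is handed out at the month-3 visit, so it cannot affect that endpoint. Phase 2 is described in the intervention group only (2.6.2), so it has no control contrast to distort.

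**6. What insurance could add.** Balancing insurance makes pairs more alike in coverage, but each pair still holds one patient with free pens and one for whom none is described. Results by insurance type would be coarse: with 30 pairs in a stratum (assumed), the half-width is 1.96 × 1.5 × √(2/30) = 0.76, far wider than the 0.05-0.20 in step 3.

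**The case against.** The strongest reply has four parts.

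- **The supply is disclosed, and its column is defensible.** Basal insulin is routine for these patients, is used per label (6.1), and the 2.3 table sorts elements of care rather than who pays. Section 1.1.1 already includes training. This stands as far as it goes, but paying for the insulin is not part of routine care as the table describes it, and no statement of the objective, aim or outcome mentions it.
- **A cost barrier among controls is not shown.** A reader might infer that controls went without insulin because of cost. The documents do not support this: they are silent on coverage, samples or assistance. That controls lacked this study's supply is a strong inference, because they were treated earlier and selected from records. That they lacked affordable insulin is not.
- **The exposure is shorter than it looks.** A reader might infer that six months of free pens bears on the primary result. It does not; only the baseline supply does.
- **The net bias has no known direction.** The design is openly non-randomized. Controls come from specialty clinics, while 3.1 allows intervention patients from primary care, which could favour the controls. This stands, and is a reason not to claim that the overall estimate is inflated.

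A reader might also expect matching on insurance to cure the problem. It cannot, and the control data listed in 2.4.1 do not mention insurance, so its availability for controls is not established.

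**Conclusion.** The point holds as one of attribution. The primary contrast estimates MDC-T with training and a free three-month insulin supply against usual care, and the plan's wording credits it to the app. That conclusion rests on the documents' description of who receives what, and needs no assumption about size.

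The size of the supply's contribution is unknown. The 0.05-0.20 range is illustrative and depends wholly on the assumed share and cost of gaps; half of ±0.40 is its extreme corner, not an estimate. The contribution could be negligible if controls had ready access to insulin. A reader might go further and infer that the trial shows nothing useful or that any benefit is due to the free insulin. The documents support neither: the package contrast remains a legitimate target, subject to the usual limits of a retrospective comparator. The change should be made because it alters what may be concluded and costs almost nothing.

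**What to change.** **Main change (wording).**

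- In the 2.3 table, show the free pen supply as a study-provided component, and correct the statement in 6.1 that only technological support and questionnaires are added to usual care.
- In 1.1.1, Aim 1, 2.4.1 and the eventual conclusion, define the contrast as MDC-T with training and free insulin supply versus usual care.
- State as a limitation that the app's contribution cannot be separated from the supply's, and that the controls' insulin costs and coverage are not known.

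**Secondary change.** Check whether insurance type is available in the EMR for controls. Where it is, add it to the propensity score in 2.6.2 to balance baseline coverage, and say explicitly that this does not remove the supply effect. Treat any results by insurance type as descriptive only.

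**Cost.** A few sentences, and one extra matching variable if the data exist. The real price is a less app-specific claim. Nothing in clinical management changes.
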